## 5. ACRONYMS, TERMS AND DEFINITIONS

Term (Acronym)	Definition
2019-nCoV	2019 Novel Coronavirus (see also SARS-CoV-2)
AE	Adverse Event
ASQ	After-Scenario Questionnaire
CDC	Centers for Disease Control and Prevention
CFR	Code of Federal Regulations
CLIA	Clinical Laboratory Improvement Amendments
COVID-19	Coronavirus disease 2019
CRF	Case Report Form
CSR	Clinical Study Report
[REDACTED]	[REDACTED]
Epic	Epic Health Research Network
ESL	Exact Sciences Laboratories
EUA	Emergency Use Authorization
FDA	Food and Drug Administration
GCP	Good Clinical Practice
IFU	Instructions for Use
IRB	Institutional Review Board
LIS	Laboratory Information System
RNA	Ribonucleic acid

	Statistical Analysis Plan: Usability Study of Home Collection and Mailing with SARS-CoV-2 Test Specimen Collection Materials (Protocol 2020-06)		
Doc. ID Number: [REDACTED]	Revision Number: 1.0	Effective Date: [REDACTED]	Page: 6 of 35

RNase	Ribonuclease
RT-PCR	Reverse transcription polymerase chain reaction
SAE	Serious Adverse Event
SAP	Statistical Analysis Plan
SARS-CoV-2	Severe Acute Respiratory Syndrome Coronavirus 2 (see also 2019-nCoV)
SARS-CoV-2 (N gene detection) Test	ESL SARS-CoV-2 (N gene detection) test [REDACTED]
SDV	Source Data Verification

## 6. STUDY DESIGN

This study is a prospective observational human factors usability study designed to evaluate the IFU in the SARS-CoV-2 Specimen Collection Materials based on the successful completion of self-collection of a nasal swab sample, which includes a valid SARS-CoV-2 test result.

At the request of the FDA, subjects with a range of education levels and ages but without medical, laboratory, or COVID-19 specimen self-collection experience are being recruited. Study volunteers are pre-screened for highest education level attained and age group. The options for highest education level attained are: no high school; some high school; high school degree only; college degree; and advanced degree. Pre-screen age groupings are <18, 18-30 (early career), 31-45 (mid-career), 46-65 (later career), >65 (nearing retirement). Pre-screening for medical and laboratory experience is focused on identifying volunteers who have experience: collecting laboratory specimens in a medical setting; preparing specimens in a medical or laboratory setting; following a protocol in a medical or laboratory setting, e.g., for laboratory testing, R&D, and quality; or, who have been trained on any process or instrumentation in a medical or laboratory setting. Subject participation is up to one day from enrollment to completion.

[figure not shown]
Subjects are considered enrolled when they provide written informed consent. Subjects who provide informed consent are observed while following the IFU for the SARS-CoV-2 Specimen Collection Materials in a setting that simulates a home environment.

After following the IFU, subjects do the following: provide feedback on the usability of the IFU by completing a survey; answer comprehension questions; provide written feedback on the experience; and, address questions from the observer about problems during use. The observer is an employee of Exact Sciences.

The specimens collected by the subjects are tested in the laboratory for SARS-CoV-2. Subjects remain blinded to the test results.

Subjects' participation is considered completed following completion of the self-survey, forms, and potential interview with the observer or at the point of early termination. The study is considered complete when approximately 30 self-collected nasal swab samples have corresponding SARS-CoV-2 test results (positive, negative, inconclusive, or invalid).

	Statistical Analysis Plan: Usability Study of Home Collection and Mailing with SARS-CoV-2 Test Specimen Collection Materials (Protocol 2020-06)		
Doc. ID Number: 	Revision Number: 1.0	Effective Date: 	Page: 7 of 35

**Figure 1:** Overview of study procedures.

## 7. ANALYSIS DATA

7.1 There are four data streams for this study: Electronic Data Capture (EDC), Epic Health Research Network (Epic), Laboratory Information System (LIS), and Laboratory Workbook. A hyperlink to the data dictionary for each data stream is available in Section 4.

- 7.1.1 Subject and observer reported surveys are collected on paper Case Report Forms (CRFs). Data are entered into an EDC system, after which they undergo source data verification (SDV). Data entry and SDV are completed by Exact Sciences. Hyperlinks to final CRFs are available in Section 4.
- 7.1.2 Laboratory results are reported via three data streams: Epic, LIS, and Lab Workbook.
  - 7.1.2.1 The Epic data stream will provide the final SARS-CoV-2 laboratory test result.
  - 7.1.2.2 The LIS data stream [REDACTED]
  - 7.1.2.3 The Lab Workbook data stream [REDACTED]
  - 7.1.2.4 Only data corresponding to the final reported result will be contained within the laboratory file transfers.

### 7.2 Observer Collected Variables

- 7.2.1 After the observer provides the SARS-CoV-2 Specimen Collection Materials, which includes the IFU, to the subject, the observer records the following information by IFU task (check one): *subject completed step with no issues; subject completed step with issues or unexpected effort; subject did not complete step or required assistance; or, not applicable*, e.g., if the subject discontinued their participation. There are three sections to the IFU that contain a total of 26 steps for specimen collection and packaging. The three sections are summarized below, and the observer records a response for each task.
  - 7.2.1.1 *Before you collect*, which includes reading the instructions (one step) and preparing for collection (two steps).
  - 7.2.1.2 *Collect your nasal swab sample*, which includes twenty steps in total:
    - 7.2.1.2.1 preparing the tube label (two steps);
    - 7.2.1.2.2 opening nasal swab (two steps);
    - 7.2.1.2.3 removing the tube cap (four steps);
    - 7.2.1.2.4 swabbing nose (two steps);
    - 7.2.1.2.5 add swap to tube (two steps);
    - 7.2.1.2.6 removing swab from tube (two steps);
    - 7.2.1.2.7 replacing the tube cap (two steps);
    - 7.2.1.2.8 placing label on tube (one step); and,

	Statistical Analysis Plan: Usability Study of Home Collection and Mailing with SARS-CoV-2 Test Specimen Collection Materials (Protocol 2020-06)		
Doc. ID Number: 	Revision Number: 1.0	Effective Date: 	Page: 8 of 35

7.2.1.2.9 washing hands and adding [REDACTED] to bag (three steps).

7.2.1.3 *Ship your kit back to the lab*, which includes placing bag in bubble wrap (one step) and placing bubble wrapped bag in box (two steps).

7.2.2 The observer records *free form notes* during their observation of the subject while the subject is completing the IFU.

7.2.3 Upon the subject's completion of both the IFU and the patient self-administered After-Scenario Questionnaire (ASQ), the observer records responses to three questions that they ask the subject about the subject's comprehension of the IFU. The observer records the subject's responses as '*correct*' or '*incorrect*' and may also record *free form text* observer comments for each of the three questions:

- 7.2.3.1 After collection a nasal swab sample, when should a person ship it to the lab?
- 7.2.3.2 How should a person store the package with the nasal swab sample inside before shipping it back to the lab?
- 7.2.3.3 What could happen to your nasal swab sample if you do not follow the steps in the IFU?

7.2.4 The observer asks the subject two general questions after assessing IFU comprehension and responses are *free form text*:

- 7.2.4.1 What information in the IFU is confusing?
- 7.2.4.2 Is there anything we could do to make it easier to collect a nasal swab sample using these materials?

7.2.5 The observer may ask the subject follow-up questions to clarify areas of misunderstanding about the IFU and to identify the root causes of tasks that the observer recorded as completed with issues or unexpected effort or not completed (did not complete or required assistance). This will be recorded as *free form text* in the comments section available for each task.

7.2.6 At study completion, the observer responds '*yes*' or '*no*' to the following three questions:

- 7.2.6.1 Did the subject experience/report Adverse Events?
- 7.2.6.2 Were any protocol deviations noted?
- 7.2.6.3 Did the subject complete the study?

7.3 Subject Reported Data

- 7.3.1 Demographic and background information: date of birth, gender, race (mark one or more options: *American Indian or Alaska Native; Asian; Black or African-American; Native Hawaiian or other Pacific Islander; White; Unknown*), ethnicity (mark one option: *Hispanic or Latino, Not Hispanic or Latino, Unknown*), and highest level of education attained (mark one option: *No high school; Some high school; High school degree only; College degree; Advanced degree*).
- 7.3.2 Prior experience with laboratory training (*yes/no*), COVID-19 specimen self-collection (*yes/no*), and COVID-19 testing (*yes/no*).
- 7.3.3 Subjects complete the psychometrically-validated three-item After-Scenario Questionnaire (ASQ) to measure their satisfaction with using the IFU to complete the sample collection [2,3].

	Statistical Analysis Plan: Usability Study of Home Collection and Mailing with SARS-CoV-2 Test Specimen Collection Materials (Protocol 2020-06)								
Doc. ID Number: [REDACTED]	Revision Number: 1.0	Effective Date: [REDACTED]			Page: 9 of 35				

	After-scenario Questionnaire (ASQ)	Strongly Agree	1	2	3	4	5	6	7	Strongly Disagree	NA
1	Overall, I am satisfied with the ease of completing the tasks in this scenario.										
2	Overall, I am satisfied with the amount of time it took to complete the tasks in this scenario.										
3	Overall, I am satisfied with the support information (online help, messages, documentation) when completing the tasks.										

7.3.4 Subjects will have the opportunity to provide written feedback on their experience by responding in *free form text* (or *checking a box if none*) to two questions:

- 7.3.4.1 What, if any, steps did you have trouble completing?
- 7.3.4.2 Do you have suggestions for improving the collection instructions?

7.3.5 Subjects will respond to IFU comprehension questions that are posed by the observer and will respond to questions about tasks completed with issues or unexpected effort, or tasks not completed. The responses to these questions will be documented by the observer in the form of *free text* (see Section 7.2).

7.4 Laboratory Data Variables

7.4.1 The specimens collected by the subject will be tested in the laboratory for SARS-CoV-2 RNA. The qualitative result for the SARS-CoV-2 test will be returned by the Epic data stream as: *positive*, *negative*, *inconclusive*, or *invalid*.

[REDACTED]

[REDACTED]

7.5 Description of Study Endpoints

7.5.1 The primary endpoint is the percentage of samples from the fully enrolled cohort to return a valid SARS-CoV-2 test result (positive, negative, or inconclusive). The target is 80% as an acceptable rate of success given the first-time task completion for minimally trained users.

7.5.2 The secondary endpoints are:

- 7.5.2.1 *Perceived usability of IFU*: The subject's self-reported satisfaction and ease of using the IFU, assessed using the ASQ. The ASQ is a valid and reliable 3-item survey on user satisfaction associated with completing a task. Item response options are on a 7-point Likert scale where 1 = strongly agree and 7 = strongly disagree. An overall satisfaction score is calculated as the average of the non-missing responses to the items (theoretical range 1-7 with a lower score indicating higher satisfaction). Endpoints from the ASQ include:
  - 7.5.2.1.1 Overall score (*continuous*), where an average of 3.5 or lower on the overall ASQ score will be considered acceptable self-reported user satisfaction.
  - 7.5.2.1.2 Categorization of overall ASQ score as 1 to 3 (indicating that the subject agrees to strongly agrees that they are satisfied) vs. 4 to 7 (indicating that the subject is neutral or strongly disagrees that they are satisfied).
- 7.5.2.2 *General comprehension of IFU*:

	Statistical Analysis Plan: Usability Study of Home Collection and Mailing with SARS-CoV-2 Test Specimen Collection Materials (Protocol 2020-06)		
Doc. ID Number: [REDACTED]	Revision Number: 1.0	Effective Date: [REDACTED]	Page: 10 of 35

7.5.2.2.1 Total out of three questions accurately answered by subject when the observer evaluates the subject's comprehension of the IFU. The questions are summarized in Sections 7.2.3.1 – 7.2.3.3.

7.5.2.2.2 Responses to individual questions.

7.5.2.3 *Problems associated with following the IFU:*

7.5.2.3.1 The total number of tasks that the subject does not complete (as opposed to completes without issues or completes with issues or unexpected effort). The 26 tasks are summarized in Section 7.2.1.

7.5.2.3.2 The total number of critical tasks that the subject does not complete (as opposed to completes with no issues or completes with issues or unexpected effort).

7.5.2.3.3 Critical tasks are outlined in Table 2 of the Study Protocol and are summarized in the table below. A hyperlink to the Study Protocol is available in Section 4. Fifteen of the 26 tasks in the IFU have been pre-specified as critical. An additional three critical tasks are assessed through the IFU comprehension questions, i.e., data collected as per Section 7.2.3.

Specimen Collection Tasks from Protocol	Equivalent in CRF (Question or task numbers match those on Observer Form)	Test Method
Read these 2 pages instructions completely	1.1 Read these 2 pages of instructions completely.	Simulated use
Plan your collection	Q#1 after collecting a nasal swab sample, when should a person ship it to the lab?	IFU comprehension questions
Prepare the tube label	2.1 Using blue or black ink, write your name, date of birth, and date and time of collection on the Collection Tube Label. 2.2 Set label aside.	Simulated use
Remove tube cap	2.5 While holding the swab, remove cap from tube.	Simulated use
Swab nose	2.9 Gently insert the entire soft tip of the swab into one nostril until you feel a bit of resistance and rub it in a circle inside the nose 4 times. 2.10 Repeat in other nostril.	Simulated use
Add swab to tube. Remove swab from tube	2.11 Remove swab from nostril and place in collection tube liquid. 2.12 Swirl in tube for 10 seconds. 2.13 Press the tip of the swab against the side of the tube to squeeze liquid from the swab.	Simulated use
Replace tube cap	2.15 Put the cap back on the tube. 2.16 Securely tighten so liquid does not leak.	Simulated use
Place label on tube	2.17 Using the completed label from Step 1, place middle of label on tube, wrap label ends around tube, stick label ends together.	Simulated use

	Statistical Analysis Plan: Usability Study of Home Collection and Mailing with SARS-CoV-2 Test Specimen Collection Materials (Protocol 2020-06)		
Doc. ID Number: [REDACTED]	Revision Number: 1.0	Effective Date: [REDACTED]	Page: 11 of 35

Place bubble wrapped bag in box	2.19 Put your tube in the bag with the absorbent pad. 3.2 Place bubble wrapped biohazard bag into Shipping box. 3.3 Remove paper backing from tape, fold box flaps closed, press to seal box closed.	Simulated use
Store sample in sealed box away from direct heat and sunlight until shipment.	Q#2 how should a person store the package with the nasal swab sample inside before shipping it back to the lab?	IFU comprehension questions
Ship package by UPS	Q#1 after collecting a nasal swab sample, when should a person ship it to the lab?	IFU comprehension questions

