4.1.2 Secondary Objective

The secondary objectives of this study are to evaluate perceived usability of the IFU as well as comprehension by the subject, identify problems (e.g., use errors, delays, close calls) that occur while following the IFU, evaluate root causes of problems, and develop strategies to mitigate those risks going forward.

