6.2 Critical Tasks for the SARS-CoV-2 Specimen Collection Materials

A Use-Related Failure Modes Effect Analysis (FMEA) approach was used to determine potential hazards and their associated risks during use of the SARS-CoV-2 Specimen Collection Materials. For each activity, the following high-level questions were asked:

- Do users correctly collect nasal swab samples?
- Do users correctly prepare samples for shipment?
- Do other aspects of use of the SARS-CoV-2 Specimen Collection Materials impact the receipt of usable nasal swab samples at ESL?
- How easy or difficult is it to understand and use the IFU in the SARS-CoV-2 Specimen Collection Materials to perform tasks?

The activities in the workflow described in the IFU were used to determine tasks to be evaluated in this usability study. Each task was then assigned a rating of “critical” or “essential,” based on a human factors risk assessment done at Exact Sciences. Critical and essential tasks are defined as follows.

- Critical tasks are those in which use errors or failure to complete would have a negative clinical impact, such as inaccurate or delayed test results.
 - Failure to successfully complete a critical task results in a use error or performance failure.
- Essential tasks represent behaviors that are important to the overall use of the SARS-CoV-2 Specimen Collection Materials but do not pose an immediate risk to the user.

CONFIDENTIAL

May not be reproduced nor disseminated outside of Exact Sciences without permission

- Failure to successfully complete an essential task will be recorded as a use error but will not necessarily result in a performance failure.

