8.3 Observation for Problems Using SARS-CoV-2 Test Specimen Collection Materials

The subject will be provided with the SARS-CoV-2 Specimen Collection Materials that include the IFU. An observer will watch the subject perform the tasks in the IFU without providing input or assistance. The observer will record the following information by IFU task:

- Completed

CONFIDENTIAL

May not be reproduced nor disseminated outside of Exact Sciences without permission

- Completed with use errors, close calls

CONFIDENTIAL

May not be reproduced nor disseminated outside of Exact Sciences without permission

- Did not complete
- Free form observational notes

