8.4 Subject Experience with SARS-CoV-2 Specimen Collection Materials

Subjects will take a survey called the After-Scenario Questionnaire (ASQ) to evaluate perceived ease of use.[3-5]

	Strongly Agree							Strongly Disagree		Not Applicable
1. Overall, I am satisfied with the ease of completing the tasks in this scenario.	1	2	3	4	5	6	7			
2. Overall, I am satisfied with the amount of time it took to complete the tasks in this scenario.	1	2	3	4	5	6	7			
3. Overall, I am satisfied with the support information (online help, messages, documentation) when completing the tasks.	1	2	3	4	5	6	7			

Figure 2: After-Scenario Questionnaire (ASQ)

Subjects will have the opportunity to provide written feedback on their experience.

Subjects will be asked questions about their experience by the observer, including their comprehension of the IFU (e.g., shipping instructions). Follow up questions to the subject by the observer may be needed to clarify areas of misunderstanding about the IFU.

Finally, the observer will ask questions to help identify the root causes of tasks observed as not completed or completed with use errors or close calls during the simulation of the IFU.

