8.6.2 Observer Reported Data

- Checklist based on workflow steps to record completion, completion with difficulty (e.g., use errors or close calls), and did not complete
- Written notes for each task
- Subject-reported answers to questions on IFU comprehension and issues following the IFU

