9.3 Other Pre-Specified Analyses

Other pre-specified analyses include a characterization of subjects' self-reported ease of use with the Specimen Collection Materials Instructions for Use (IFU), acceptable answers on general comprehension of the IFU, observer-reported problems associated with following the IFU, [REDACTED] [REDACTED] and evaluation of root causes of problems associated with user tasks, including but not limited to critical tasks. All analyses will be descriptive in nature. Frequency and percentage will be calculated for categorical measures and mean, standard deviation, median, and interquartile range will be calculated for continuous measures.

The subject's self-reported satisfaction and ease of using the IFU will be assessed using the After-Scenario Questionnaire (ASQ).[3, 4] The ASQ is a valid and reliable 3-item survey on user satisfaction associated with completing a task. Item response options are on a 7-point Likert scale where 1 = strongly agree and 7 = strongly disagree. An overall satisfaction score is calculated as the average of the non-missing responses to the items (theoretical range 1-7 with a lower score indicating higher satisfaction). The frequency and percentage of each response to all questions will be presented, along with the mean, standard deviation, median, and interquartile range of the overall score. In addition, the frequency and percentage of subjects with an overall score of 1 to 3 (indicating that the subject agrees to strongly agrees that they are satisfied) will be presented. An average of 3.5 or lower on the overall ASQ score will be considered acceptable self-reported user satisfaction.

The frequency and percentage of correct vs. incorrect responses from the subject on questions around shipping and invalid tests consequences will be presented.

The frequency and percentage of individual problems observed (by an external observer) with the Specimen Collection Materials IFU will be presented, along with the distribution of total number of problems overall and total number of problems on critical tasks (**Section 6.2**).
[REDACTED]
[REDACTED]

A qualitative evaluation of results from the user reported data, external observer feedback on user interactions, and laboratory testing will be conducted to assess the root cause of problems and evaluate mitigating solutions, e.g., whether specific parts of the IFU should be modified.

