8.2.3.1 The n, mean, standard deviation, median, and interquartile range of total number of tasks that the subject does not complete (as opposed to completes without issues or completes with issues or unexpected effort) will be calculated, overall and for the subset of fifteen critical tasks from the IFU. The frequency and percent of total problems in categories of 5-unit increments will also be reported. This will be presented for the subset of patients for whom the observer was able to observe the subject attempt all tasks. Subjects where the observer responded “not applicable” to one or more tasks will not contribute to this analysis.

8.2.3.2 The frequency and percentage of each observer-response to all 26 tasks will be presented.

8.2.3.3 Critical tasks will be explicitly labeled for easy identification.

8.2.4 *Root causes of problems that occur while following the IFU:* A qualitative evaluation of listings from the user reported data, external observer feedback on user interactions, and laboratory testing will be conducted by Clinical and Regulatory Affairs to assess the root cause of problems and evaluate mitigating solutions, e.g., whether specific parts of the IFU should be modified. The listings will be provided by Clinical Biostatistics to Clinical and Regulatory Affairs, presented by question within data stream. Critical tasks will be explicitly labeled for easy identification. Post-hoc analyses may be performed at the request of Clinical and Regulatory Affairs to help summarize their assessment of root cause issues.

8.2.5 The final secondary objective is to develop strategies to mitigate problems occurring while following the IFU. This does not have an associated statistical endpoint or quantitative analyses.

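### SAP 8.2.3.1 labels a count of tasks not completed as total problems, and no visible table gives a per-subject total that includes tasks completed with use errors or close calls

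*SAP*

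**What the plan says.** **Protocol.** The secondary objective (4.1.2) is to "identify problems (e.g., use errors, delays, close calls) that occur while following the IFU". The observer grades each task, and one grade is "Completed with use errors, close calls" (8.3); section 8.6.2 describes the same checklist as recording "completion with difficulty (e.g., use errors or close calls), and did not complete". Section 8.4 has the observer ask about the "root causes of tasks observed as not completed or completed with use errors or close calls during the simulation of the IFU". For analysis, section 9.3 promises the frequency of individual problems, "along with the distribution of total number of problems overall and total number of problems on critical tasks". It does not define a problem at that point. Section 6.2 says "Failure to successfully complete a critical task results in a use error or performance failure", which links use error to failure to complete.

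**SAP.** Section 7.2.1 has four grades: completed without issues; completed with issues or unexpected effort (the middle grade below); not completed or assistance required; and not applicable. Under the heading on problems with following the IFU, 7.5.2.3.1 and 7.5.2.3.2 define the two totals as tasks not completed. For critical tasks the wording is "critical tasks that the subject does not complete (as opposed to completes with no issues or completes with issues or unexpected effort". Section 8.2.3.1 summarises these totals and adds: "The frequency and percent of total problems in categories of 5-unit increments will also be reported". The shells for Tables 8 and 9 follow the same definition. SAP 7.5.2.3.4 and 8.2.3.2 separately plan the distribution of grades for each task, which is Table 10.

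**The concern.** The protocol's problems include errors made on tasks that were completed. The SAP's totals exclude those tasks but keep the broader label. The SAP is also not consistent within itself: 7.2.5 seeks root causes for both the middle grade and non-completion, and Table 10, whose title refers to observed problems, has a column for the middle grade.

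Identifying problems is a secondary objective, and Tables 8 and 9 are its only visible per-subject summaries. They could show zero while errors on critical tasks are common, if observers grade those errors as completed with issues. Protocol Table 2 links poor swabbing, rubbing, swirling and pressing to invalid, false inconclusive or false negative results. The protocol adds that false negatives are not anticipated, because a negative result still needs the RNase P signal.

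**Working it through.** **1. Task counts.** The steps in SAP 7.2.1 are 3 + (2+2+4+2+2+2+2+1+3 = 20) + 3 = 26. The critical tasks in SAP 7.5.2.3.3 and Table 10 are 1.1, 2.1, 2.2, 2.5, 2.9 to 2.13, 2.15 to 2.17, 2.19, 3.2 and 3.3, which is 15. Both stated figures reproduce.

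**2. What the definition does to a subject's score.**

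| Subject | Table 8 count | Count including the middle grade |
|---|---|---|
| 26 tasks with issues, 0 not completed | 0 | 26 (15 on critical tasks) |
| 10 tasks with issues, 1 not completed | 1 | 11 |

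**3. Whether Table 10 fills the gap.** It does not. Take 30 subjects. In case A, one subject has issues on all 26 tasks. In case B, 26 subjects have one issue each, on different tasks. Table 10 shows one issue per task in both cases, yet the per-subject distributions are opposite: a maximum of 26 in 1 subject, against a maximum of 1 in 26 subjects. Table 10 also lacks valid and invalid columns, although SAP 8.2.3 says problems will be described by test result. Listings 1-26 hold each subject's grade and test result, but they are line listings and not a distribution.

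**4. Illustration of size.** The documents give no error rates and no visible rule for grading a partly performed step, so the rates here are assumptions. Take the four steps that match errors in Protocol Table 2 (2.9, 2.10, 2.12, 2.13), with independent error probability p per step and a fraction q of errors graded as completed with issues.

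- Subjects with at least one error: 1 − (1 − p)^4
- Subjects shown in Table 9: 1 − (1 − p(1 − q))^4
- Missed: the difference

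| p | At least one error | Of 30 | Missed, q = 0 | Missed, q = 0.5 | Missed, q = 1 |
|---|---|---|---|---|---|
| 0.02 | 7.8% | 2.3 | 0 | 3.8 points (1.1 of 30) | 7.8 points |
| 0.05 | 18.5% | 5.6 | 0 | 8.9 points (2.7 of 30) | 18.5 points |
| 0.10 | 34.4% | 10.3 | 0 | 15.8 points (4.8 of 30) | 34.4 points |

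For p = 0.05 and q = 0.5: 1 − 0.95^4 = 18.5%, and 1 − 0.975^4 = 9.6%, so 8.9 points are missed. If errors fall entirely in the same subjects, 18.5% drops to 5%, or 1.5 of 30.

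**The case against.** The SAP states its narrower count openly, and Protocol 9.7 lets the SAP supersede protocol methods. Protocol 9.3 leaves problems undefined, and 6.2 ties use error to non-completion. Counting only the more severe grade while seeking root causes for both is a coherent choice. Table 10 already gives the middle grade for every task with critical tasks marked, the titles of Tables 8 and 9 say plainly that they count tasks not completed, and SAP 8.2.4 allows post-hoc summaries. The middle grade includes unexpected effort, so a combined count would give mild difficulty the same weight as failure. The assumed rates have no source. Some of the chosen errors, such as skipping the second nostril or not pressing the swab, are omissions that an observer would naturally grade as not completed, and Table 9 would count them.

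Much of this stands. The middle grade is measured and reported, what is missing is one aggregation, and the illustration cannot fix the size. But permission to supersede does not explain why the broader label was kept, and the visible text gives no reason for the narrowing. Post-hoc permission is not pre-specification of a distribution that the protocol did pre-specify. The weighting problem is met by showing both counts.

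**Conclusion.** The concern holds. SAP 8.2.3.1 uses the name total problems for a narrower quantity, and no visible planned table gives a per-subject total that includes tasks completed with issues. This is limited to visible tables, since the content of Tables 11-13 is redacted.

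The one firm figure follows from the definitions: issues on every task score 0 of 26 and 0 of 15. Beyond that, the gap depends on grading practice. Under the assumed error rates it runs from nothing to 34.4 percentage points of subjects. The analysis is secondary and descriptive, and the primary endpoint does not change. The change is worth making before analysis because it lets the study report the distribution behind its own secondary objective.

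**What to change.** - In SAP 8.2.3.1, replace the label total problems with tasks not completed.
- Add to Tables 8 and 9 a second block of per-subject totals of tasks either completed with issues or unexpected effort, or not completed, in the existing overall, valid and invalid columns. Keep the present block.
- In the new block of Table 9, give n (%) of subjects with at least one such critical task.
- State in SAP 7.5.2.3 that the new block is the closest available measure of the Protocol 9.3 distribution but not identical to it, because the middle grade also covers unexpected effort and each task is graded once.

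The cost is SAP wording and extra table rows. The grades are already on the observer form and go into the combined analysis file (SAP 7.6.1.3), so no new data are needed. The drawback is that the broader count takes in mild difficulty and will look less favourable; presenting it beside the narrower count deals with that.
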